10. AUDIO/VIDEO RECORDINGS

YST+YM interactive sessions and semi-structured feedback interviews will include audio-video recordings, collected via URMC supported video conference software (e.g., Zoom). These recordings will be labeled only with a code number, which will be kept in a URMC supported HIPAA-compliant data storage platform (Box.com). These recordings will be used to evaluate intervention fidelity and patient engagement with the intervention, as well as for further refinement of the intervention content.

11. RISKS TO SUBJECTS

Research assessments: During self-report questionnaires and semi-structured interviews, the primary risk is invasion of privacy (including because study staff may utilize phone and email reminders of assessment visits), breach of confidentiality (if safety issues are detected), or mild reactions of distress or fatigue. Given that assessments and intervention may be conducted in the subjects' homes (i.e., during remote administration via phone or Zoom), others could be present and there is a risk of revealing the subject's participation in the study to members of the household who were not otherwise aware. Subjects will have full discretion in having others

Page 16 of 64 Version Date: 12/13/21 present. All assessment measures and procedures have been safely used in previous research with psychiatric populations and have been reviewed by experts in the treatment of acutely suicidal adolescents at URMC. No sustained negative effects from assessments are expected, but negative outcomes cannot be ruled out.

Intervention: The primary risk of participation in YST+YM is emotional distress or fatigue. Although YST+YM is an adjunctive, strengths-based intervention with a positive emphasis, youth and adult support subjects may still think about stressors and negative life events. They will receive support from the YST+YM interventionist for such experiences. No sustained negative effects are expected, but negative outcomes from behavioral interventions cannot be ruled out. The study PI ([name]) has an active limited permit to practice psychotherapy under a Co-I ([name]) and the PI will be a fully licensed clinical psychologist by October 2021. The PI will provide weekly (and as needed) clinical supervision YST+YM interventionists. [name] has experience working with psychiatrically distressed adolescents and adults, including those with active suicide risk and will be on-call at all active study times (i.e., URMC business hours, when the intervention is being administered) to support interventionists and subjects as needed.

Recordings: Audio recordings of semi-structured interviews will be transcribed and then destroyed to protect the security and confidentiality of identifiable information. In order to protect subjects' **privacy**, audio-visual recordings will only be made with subjects' written assent / consent; subjects will be free to refuse to answer any questions they would prefer to not answer; interviews will be conducted in private settings. The data on the recording will be identified only by an ID number. Recordings for sessions will be uploaded onto UR Box.

Coercion / Vulnerable Subjects: Some subjects in the study will be minors who were recently placed in partial psychiatric hospitalization for suicide-related concerns. Their age and their expected level of mental health distress make them vulnerable to coercion (e.g., coercion to participate in the study). We take several precautions to minimize this risk, including utilization of study personnel with prior mental health training, the presence of the subject's current mental health therapist who is reminded to instruct the patient their participation will not affect their non-study care (which consultation with clinic staff has revealed is typically soothing to the patient), and the additional requirement that the subject's parent or legal guardian consent to their participation.

Minimization of Risk:

- Informed Assent / Consent: All study team members must read and understand the study protocol, the informed assent / consent forms, and the case report forms prior to being involved in the informed consent process. The PI will practice the consent process with the consent designee(s) prior to the enrollment of the first subject. The PI will train the study staff to conduct consent by explaining, demonstrating, and observing the consent process until they master the consent process. The PI will randomly check the consent process quarterly and re-train staff as needed. Before the written consent, a verbal consent will be obtained in the stage of phone screening.
- The Certificate of Confidentiality (CoC) automatically granted to the research team from the National Institutes of Health (NIH) in order to further protect the privacy of the subjects involved in this research. The CoC will allow the research team to refuse to disclose subjects' identifying information (including sensitive health information assessed in this study such as their psychiatric diagnoses or self-injurious thoughts and behaviors) in the unlikely event of any civil, criminal, administrative, legislative, or other proceedings.
- Risks associated with **emotional distress or fatigue** will be minimized by employment of research personnel with appropriate backgrounds and experience and work with psychological factors. All assessments will last approximately 30 60 minutes. Subjects

Page 17 of 64 Version Date: 12/13/21 will be reminded that if they become fatigued, they may terminate the assessment at any time.

- During the course of assessment interviews, study staff will monitor subjects' reactions for signs of distress or fatigue. If necessary, subjects may take breaks from the assessment before completing it.
- If a subject's safety becomes a concern, the researcher will evaluate the subject's emotional state and safety. If the subject appears distressed, study staff will briefly attempt to de-escalate the patient's distress. If these measures do not effectively reduce the patient's distress within 10-15 minutes and depending on the severity of the patient's distress, study staff will call [name] (or the person covering for him), who will maintain a cell phone for this purpose. In case of an emergency, study staff will call 9-1-1.
- Given that we will be assessing suicidal ideation and attempts for youth 0 subjects and that youth subjects may report these outcomes, study staff will be trained in the study's safety protocol for mental distress and suicide risk, which involves items from the Columbia Suicide Severity Rating Scale and clinical interview. Note, adult support team subjects will never be asked questions about any mental or physical health outcomes, only about the feasibility and acceptability of the intervention. Youth subjects will be informed that study staff will perform an immediate evaluation of their dangerousness towards self or others should safety concerns arise during assessments or treatment sessions. Subjects will also be informed that their confidentiality may be breached should concerns arise about their dangerousness to self or others. Any endorsements of suicidal planning or recent suicide attempt will involve notifying [name] for review of risk and protective factors and consideration of appropriate steps. including (but not limited to) safety planning, contacting therapist or primary care provider, contacting mobile crisis team, emergency psychiatric services, or hospitalization within 24 hours. Subject providers will be notified of elevated risk. [name] has expertise in suicide among high-risk populations. While it is expected that most subjects for the current study (given inclusion criteria of passive or active ideation in the past month) will report significant distress and suicide ideation, staff will be trained in the study's safety protocol and data from each assessment will be reviewed with [name] weekly, or more often if needed. Finally, subjects will be informed that suspected child abuse will be reported, as mandated by law. Situations involving potential imminent dangerousness may involve the use of emergency services and law enforcement authorities. This safety protocol has been modelled after previously successful protocols utilized by a co-investigator ([name]).

Alternatives to participation: if the youth subject elects not to participate in the study, they will simply proceed to treatment as usual (as recommended and implemented by CAPHS staff). There are no alternatives to participation for parents / legal guardians or adult support team subjects.

12. POTENTIAL BENEFITS TO SUBJECTS

In a similar study population of acutely suicidal adolescents, traditional YST reduced all-cause mortality by 50% over the subsequent 10 years.¹⁵ Because our study intervention (YST+YM) includes a full administration of traditional YST, it is likely some youth subjects may experience reduced risk of suicide attempt or longer term risk of all-cause mortality as a result of participation in the study. Because the study intervention further targets social support surrounding youth, which is known to have anti-depressive and anti-anxiety effects, youth subjects may also experience improved mood and emotional state over the course of the study.²⁻⁵ There are no direct benefits of the intervention for parents / legal guardians or adult support team subjects. For all subjects, it is possible the assessment portion of this study may

Page 18 of 64 Version Date: 12/13/21 provide benefit by facilitating subjects' learning about themselves.

13. COSTS FOR PARTICIPATION

All subjects will be responsible for all fees charged by their carrier's service plan for text messaging. This research study will not reimburse subjects for any increased charges, data usage against plan limits or changes to data fees from the research texts. However, because the entire study involves under 50 total text message prompts per subject, it is unlikely subjects will incur meaningful costs beyond what they were already paying for cell-phone service.

14. PAYMENT FOR PARTICIPATION

Youth subjects will receive \$100 in Amazon.com e-gift cards for completing the entire study. These will be administered in \$25 increments after each of the four assessment points in the study. Because each assessment lasts approximately 1 hour total, this compensation rate roughly translates to \$25 an hour for each subject's time.

Compensation will be prorated according to the assessment points completed. For example, a subject dropping out after completing the first three assessment points (baseline, treatment midpoint, post-test) would receive the first three \$25 payments at the time of those assessments. However, they would not receive the final payment for the assessment they did not complete.

Participation as a parent / legal guardian or an adult support team subject is voluntary and will not be monetarily compensated.

Compensation for participation is the same for subjects in both phases.

15. SUBJECT WITHDRAWALS

Youth psychiatric re-hospitalization: Subjects will be withdrawn from the study and from treatment if they are hospitalized for psychiatric concerns (e.g., suicide attempt, manic episode). Under these conditions subjects (a) will likely be in sufficient distress that they can no longer maintain assent for participation and (b) require more immediate and intensive care than is appropriate for subjects in YST+YM. Non-psychiatric hospitalization (e.g., broken bone, chronic medical condition) will not trigger withdrawal from the study.

Youth failure to complete treatment: Youth subjects will have 14 weeks from the time of discharge to complete the 3 sessions of the YM module in the YST+YM treatment. Patients that have not completed these three sessions after 14 weeks will have their treatment terminated, but will still be allowed to complete any remaining assessments in the study.

Parent / legal guardian withdrawal: Any parents / guardians who wish to withdraw from the study will be allowed to do so at no penalty to themselves or their children. If a parent / guardian wished to withdraw but still allow their child to participate, that youth will still be allowed to continue independently.

Adult failure to complete treatment: Adult support team subjects will have 14 weeks from the time of discharge to complete the 12 YST-based phone check-in sessions with study staff. Subjects that have not completed these sessions after 14 weeks will have their support team role terminated, but will still be allowed to complete any remaining assessments in the study.

Failure to establish adult support team: The YST+YM intervention requires community adults

Page 19 of 64 Version Date: 12/13/21 to commit to providing 12 weeks of social support to a teen in psychiatric distress. Even when the youth subject makes several nominations, it is possible none of the adults they nominated will be able to join the intervention. If study staff are unable to confirm at least one supportive adult is willing to serve on a subject's support team by 2 weeks after the patient's discharge date, that subject will be withdrawn from the study.

Partial withdrawal: Subjects who wish to withdraw from the intervention, but continue assessments will be allowed to do so. They will be compensated at the same rate for all remaining assessments. Subjects who wish to withdraw from the assessments, but remain in the intervention will be allowed to do so. However, they will only be compensated for assessments they have already completed. Attempts will be made to add a replacement subject to the study in all of these cases, as long as there is sufficient funding and study time remaining to do so.

Data use after withdrawal: Unless otherwise requested by the subject at the time of withdrawal, all available data will be retained and integrated into subsequent analysis.

Sample size maintenance: Study staff will attempt to replace any withdrawn youth subjects with the next available patient - as long as there is sufficient time remaining in the study (i.e., at least 6 months) for new subjects to complete the intervention and all assessments. No replacement attempts will be made for adult support team members who withdraw.

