Aim 1 - To optimize YST+YM for feasibility and acceptability. Outcome: Semi-structured interviews and rating scales will identify the most and least preferred elements of the YM module. Response rates to automated text-messages will also be used to evaluate message appeal.

Aim 2 - To test target engagement: does YST+YM increase utilization of interpersonal emotionregulation strategies and social support among adolescents with recent suicidal ideation or attempts? Hypothesis: over 12 weeks of YST+YM, subjects will demonstrate increases in: (a) the number of weekly contacts initiated to supportive adults in their lives, (c) the utilization of interpersonal emotion regulation strategies, and (c) their perceived sense of social support. These gains will be maintained at 3-month post-intervention follow-up.

Aim 3: Estimate prevalence of clinical outcomes for planning of subsequent trials - what is the average rate of clinical over the course of intervention and through 3-month follow-up? Outcome: Estimates of changes in distal targets, including anxiety, depression, and suicidal ideation and attempts for the planning of larger subsequent trials.

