4. STUDY DESIGN

This study is a two-phased, one-armed pilot trial to evaluate feasibility, acceptability, and target engagement of YST+YM. It will also facilitate estimation of clinical outcome prevalence, including suicidal ideation and attempts over the intervention period and through post-intervention follow-up.

In phase one (content refinement; n = 5-10), feasibility and acceptability will be optimized via measures of subject engagement with the intervention (i.e., text-message response rates) and with subject feedback during semi-structured interviews. We will also assess feasibility of the assessments used to measure emotion regulation, perceived social support and connectedness, and clinical outcomes (i.e., anxiety, depression, and suicidal ideation and attempts).

In phase two (pilot; n = 60-70), target engagement and prevalence of clinical outcomes will be addressed, as well as continued assessment of feasibility and acceptability of YST+YM. Consistent with specific aims above, intervention targets include engagement with treatment (i.e., initiating contact with support team members), changes in emotion regulation skills, and perceived social support and connectedness. Distal targets, including anxiety, depression, and suicidal ideation and attempts will also be assessed to establish point estimates for power analysis and sample size planning in future trials. Subject engagement with the intervention and feedback during semi-structured interviews will be used to assess feasibility and acceptability of YST+YM (following initial modification in response to phase one subject feedback).

Because the intervention lasts approximately three months per subject, the phases will be staggered, such that some subjects will be enrolled in phase two before all phase one subjects have completed their entire intervention course. For example, we anticipate that n = 5-10 phase one subjects may complete the first remote session of YST+YM within 6 weeks of the study start date. Because we collect feedback immediately following each session, this means we will have received all the information required to finalize that session's outline and content for the launch of phase two – even though these phase one subjects will have several weeks left of YST+YM overall.

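### A suicide attempt can end a youth's study assessments, and the Aim 3 analysis does not say that this attempt is counted, so the attempt rate is at risk of being understated

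*Combined protocol and SAP*

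**What the plan says.** Section 15 (Subject Withdrawals) sets the rule for psychiatric re-hospitalisation: "Subjects will be withdrawn from the study and from treatment if they are hospitalized for psychiatric concerns (e.g., suicide attempt, manic episode". It gives two reasons. Such youth "will likely be in sufficient distress that they can no longer maintain assent for participation", and they need more intensive care than this intervention offers.

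Other departures in the same section are handled differently. Youth who have not finished the three sessions by 14 weeks "will have their treatment terminated, but will still be allowed to complete any remaining assessments in the study". For voluntary departures, "Subjects who wish to withdraw from the intervention, but continue assessments will be allowed to do so".

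Two further rules there bear on the analysis. Unless the subject asks otherwise, "all available data will be retained and integrated into subsequent analysis". On sample size, "Study staff will attempt to replace any withdrawn youth subjects with the next available patient", if enough study time remains.

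Attempts are an outcome. Aim 3 in section 2 calls for "Estimates of changes in distal targets, including anxiety, depression, and suicidal ideation and attempts for the planning of larger subsequent trials", and section 4 says: "Distal targets, including anxiety, depression, and suicidal ideation and attempts will also be assessed to establish point estimates for power analysis and sample size planning". Table 2 in section 9 places the attempt questions in the youth survey, given at the three sessions and at weeks 22-24, with the C-SSRS straight after it. The Aim 3 analysis in section 17 is one sentence, promising means and proportions. Section 5 says attrition will be handled by intent-to-treat. Section 16 (Data and Safety Monitoring Plan) refers to an attached plan.

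**The concern.** Ordinary dropout loses youth for many reasons. Here one route out of the study can be the very event that Aim 3 is meant to estimate. A youth admitted after an attempt reaches no later survey, and the survey is where the available text collects attempts. If the triggering attempt is not carried into Aim 3 by some other route, the youth most likely to have attempted contribute no event.

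Aim 3 exists to supply planning figures. An attempt rate that is too low could lead the next team to plan a larger trial than it needs, or to set attempts aside as too rare to use as an outcome. The week-12 and week-24 means for depression and ideation would also describe only youth who were not withdrawn.

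**Working it through.** **What the plan's figures allow.** The documents give no expected attempt rate for this trial, so there is none to reproduce. The nearest figure is the follow-up sample in section 5: 65 × (1 − 0.25) = 48.75, consistent with the stated 50. Nothing says whether 65, about 50 or some other number is the Aim 3 denominator.

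**Tracing one event.** Take a youth who attempts in week 8 and is admitted.

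1. Section 15 withdraws the youth from the study, so the week-12 and week-24 surveys do not take place.
2. The last survey, at about week 6, predates the attempt.
3. Staff must know of the admission to apply the rule, so some record may exist.
4. Section 17 does not say that this record feeds the attempt proportion, or whether the youth stays in the denominator.

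**Size, as an illustration.** Inputs:

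- One-year attempt rate r. Section 2 gives 30% for youth hospitalised for attempts. Section 6 also admits youth with ideation alone, so 10% and 20% are added as assumptions.
- Constant hazard over the year (assumption).
- s, the share of attempters whose triggering attempt is uncounted. The documents give no value. 25% and 50% are assumptions, and s = 0 if every such attempt is logged and counted.
- Denominator: all 65 enrolled.

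The 24-week risk is p = 1 − (1 − r)^(24/52), and the rate read is p(1 − s). For r = 0.30, p = 1 − 0.70^(24/52) = 0.152, or 65 × 0.152 = 9.9 attempters.

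| One-year rate | 24-week risk | Read if 25% uncounted | Read if 50% uncounted |
|---|---|---|---|
| 10% | 4.7% | 3.6% | 2.4% |
| 20% | 9.8% | 7.3% | 4.9% |
| 30% | 15.2% | 11.4% | 7.6% |

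The relative understatement equals s in every row.

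**A limit on s.** Weekly calls to support adults run for 12 weeks, and Table 1 lists no contact between weeks 12 and 22. At r = 0.30, the share of 24-week attempts falling in that gap is (0.70^(12/52) − 0.70^(22/52)) / 0.152 = (0.921 − 0.860) / 0.152 = 0.40. An admission then may go unknown, in which case no withdrawal happens and the youth can still report the attempt at weeks 22-24. Unless staff hear of gap admissions another way, s could not exceed about 60%, even if every other attempter were admitted and none were counted.

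**Sampling error.** Ten of 65 is 15.4%, with an exact 95% interval of 7.6% to 26.5%. The 11.4% reading is well inside it, and the 7.6% reading sits at its lower limit.

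**Why an all-enrolled denominator is not enough.** If the expected 25% attrition supplied no post-baseline information, a true 15.2% would read 0.152 × 0.75 = 11.4% even with every known attempt counted. The proportion over all enrolled is therefore a minimum.

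**The case against.** The best defence is that the event may already be recorded. Staff cannot apply the rule without learning of a psychiatric admission. Section 15 keeps available data for analysis, intent-to-treat ordinarily means all enrolled youth, and section 11 sends endorsed recent attempts to a named reviewer. The attached safety plan is where such admissions would normally be logged.

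Much of this stands. A reader might infer that triggering attempts will be lost and the rate will be too low. The documents do not support that: they leave open whether the attempt is counted, and the safety plan was not available. What remains is that retaining data does not make a staff-learned admission an Aim 3 event, and intent-to-treat sets no Aim 3 denominator. Even with all 65 in the denominator, an uncounted attempt lowers the rate.

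A second objection is that full withdrawal protects the youth and rests on assent. That is a fair reason, and the main fix leaves the rule alone. A reader might also infer that the rule itself is wrong. Nothing here shows that, and no position is taken on stopping treatment.

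Third, in a pilot of about 65 the sampling error is wide enough to cover much of the illustrated bias. That limits the urgency. But an interval shows its own width, whereas an unstated counting rule is invisible to whoever uses the estimate.

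**Conclusion.** The concern holds as a risk. Followed as written, the withdrawal rule makes loss to follow-up depend on an Aim 3 outcome, and the available text does not repair this in the analysis. The direction is towards understatement of the attempt rate, by the share of triggering attempts left uncounted. That share is unknown and may be zero. The 11.4% and 7.6% readings rest on the 30% one-year rate applying here, a constant hazard, and assumed shares of 25% and 50%; they are not forecasts. Later means for depression and ideation omit withdrawn youth in any case. This deserves correction before Aim 3 is analysed, but it does not threaten the trial.

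**What to change.** **Main change, in section 17.**

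- Count an attempt that leads to a withdrawing hospitalisation as an Aim 3 event, taking its date and reason from the withdrawal or safety record. If the Data and Safety Monitoring Plan already logs this, cite it.
- Report the proportion of all enrolled youth with at least one attempt between baseline and week 24, counting replacements as additional enrolments. State that it is a minimum.
- Report beside it the number whose week-24 status is unknown, by withdrawal reason.
- Add an estimate that allows for time at risk, such as a Kaplan-Meier proportion or a rate per person-time, with the triggering attempt as an event. Attempts reported in the survey then need a date, or at least the assessment interval. Note that censored youth, especially those withdrawn for other psychiatric admissions, may not share the risk of those who remain.
- State that later symptom and ideation means exclude withdrawn youth.

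The cost is protocol wording, a log field if none exists, and a little analysis work. No assessments are added.

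**Optional change, in section 15.** Separate leaving the intervention from leaving the assessments. Offer re-hospitalised youth the remaining assessments only where assent or consent, and parental permission where required, is re-confirmed. The protocol and consent forms would have to provide for that approach. The cost is at most three assessments per youth, each paid at $25 and lasting about an hour with live staff and safety review. Some youth will decline.
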